## 6.3 Data Derivations based on Timing

For a given date within the screening period, the sequence number identifying the study day will be computed as the relevant screening date minus the date of Day 1 (i.e., screening date – date of Day 1). For a given date on/following infusion with Thrombosomes, the sequence number identifying the study day will be computed as the relevant infusion (or post-infusion) date minus

the date of Day 1 plus 1 day (i.e., infusion or post-infusion date – date of Day 1 + 1) to allow for inclusion of Day 1 within the computed period.

The following will define prior medication use versus concomitant medication use:

- Prior medication – any medication last used by a patient within the 4 weeks immediately preceding the date of Thrombosomes infusion. Anti-coagulant medications represent an exception, with the applicable range in dates ending at 48 hours before infusion.
- Concomitant medication – any medication taken on or after the date of Thrombosomes infusion through the Day-6 visit. Anti-coagulant medications represent an exception, defined as concomitant if taken at any time during the 48 hours preceding infusion through the Day-6 visit.

Baseline values for all assessment variables will be based on data collected during the latest assessment procedure performed prior to infusion with Thrombosomes. Unless otherwise specified, the change-from-baseline (CFB) value corresponding to any quantitative post-infusion assessment variable will be calculated by subtracting the baseline assessment value from the relevant post-infusion assessment value. If either the baseline or post-infusion assessment value is missing, then the CFB value will also be set to missing.

Pre-treatment AEs and treatment-emergent AEs (TEAEs) will adhere to straightforward definitions, with pre-treatment events occurring prior to start of the Thrombosomes infusion on Day 1 and treatment-emergent events occurring at or following the start of infusion.

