## 2 STUDY OBJECTIVES AND ENDPOINTS

### 2.1 Study Objectives

#### 2.1.1 Primary Objective

The primary objective of this study is to assess the effect of escalating infusion doses of Thrombosomes on the safety of actively-bleeding, thrombocytopenic patients.

Three dose levels, including 5 mL ( $9.45 \times 10^7$  particles/kg or 165 thrombin generation potency units [TGPU] per kg), 10 mL ( $1.89 \times 10^8$  particles/kg or 330 TGPU/kg), and 20 mL ( $3.78 \times 10^8$  particles/kg or 660 TGPU/kg), will be studied across 3 sequentially enrolled patient cohorts. Incidence of treatment-emergent adverse events (TEAEs) and serious adverse events (TESAEs), application of suspension or stopping rules, and abnormality or worsening in measures of bleeding severity, coagulation, hematology, serum chemistry, vital signs, and cardiac, physical, and neurologic statuses will be used as indicators of safety.

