## 2.2 Study Endpoints

### 2.2.1 Primary Endpoints

Several primary endpoints will be quantified per patient cohort (i.e., by dose level), as well as overall (i.e., across all 3 dose levels):

- Overall frequency of (and number and percentage of patients who experience) TEAEs and TESAEs, including serious adverse drug reactions and treatment-related events specifically defining the study's suspension and stopping rules (i.e., thromboembolic events, acute lung injury, anaphylaxis, and death).
- Numbers and percentages of patients by highest WHO bleeding severity grade at baseline and post-baseline time-points, by highest severity grade at post-baseline time-points relative to baseline (allowing for assessment of shift), by both highest severity grade and bleeding site at baseline and post-baseline time-points, and by indication of a maximum severity grade  $\geq 2$  across bleeding sites at post-baseline time-points.
- Numbers and percentages of patients by grade-level change in WHO bleeding severity (e.g., -2, -1, 0, +1, +2, +3) from baseline to post-baseline time-points for the patient's most severe bleeding site at baseline, by indication of increased bleeding severity from baseline to post-baseline time-points for the patient's most severe bleeding site at baseline, and by indication of newly-developed bleeding sites from baseline to post-baseline time-points.
- Statistics describing (and/or graphics showing) central tendency and variability in coagulation, hematology, and serum chemistry measures across patients at baseline and post-baseline time-points, allowing for assessment of directional change in measures over time.
- Number and percentage of patients who shift from normal or clinically non-significant abnormal findings to clinically significant abnormal findings in coagulation, hematology, or serum chemistry measures between baseline and post-baseline time-points.
- Statistics describing central tendency and variability in vital signs, oxygen saturation (per pulse oximetry), and select 12-lead electrocardiogram (EKG) measures across patients at baseline and post-baseline time-points.
- Number and percentage of patients who shift in category of overall EKG interpretation from normal or clinically non-significant abnormal to clinically significant abnormal between baseline to post-baseline time-points.

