### 3.2 Safety Assessments

The Primary Objective of this study is to assess patient safety across increasing infusion dose levels of Thrombosomes. This will be principally achieved by monitoring patterns in the incidence of AEs and, in particular, SAEs. An AE is any untoward or unfavorable medical occurrence in a study subject that does not necessarily have an underlying relationship with the investigational product. An AE can be any undesirable sign (e.g., an abnormal physical exam or laboratory finding), symptom, or disease, temporally associated with use of the investigational product. As described in Section 2.2.1, Primary Endpoints, safety assessments supporting the identification of AEs will include:

- Coagulation measures.
- Hematology measures.
- Routine serum chemistry measures.
- Special serum chemistry measures (troponin).
- Vital signs, plus pulse oximetry readings.
- 12-lead EKG measures.
- Physical/neurologic status.

All AEs will be described by (a) timing of the event relative to infusion start (pre-treatment AE vs. treatment-emergent AE [TEAE]), (b) system organ class (SOC) and preferred term (PT) per version 20.0 of the Medical Dictionary for Regulatory Activities (MedDRA), (c) seriousness of the event (i.e., classification as SAE), (d) criteria satisfied for SAE classification, (e) severity of the event, (f) relationship with the underlying disease, and (g) relationship with the investigational product. While data will be reported for all AEs documented within the study (i.e., both non-serious and serious), data describing all AEs will be analyzed through the Day-6 visit, and data specifically describing SAEs will be analyzed through the Day-30 visit.

An SAE is an AE that may be significant enough to lead to changes in the way the investigational product is developed or administered (e.g., adjustment to dose levels, target population, monitoring schemes, and patient consent forms). Furthermore, an SAE may result in any of the following outcomes, which, in this study, represent criteria for AE categorization as “serious”.

- Death
- Life-threatening situation (patient is at immediate risk of death)
- In-patient hospitalization (excluding those for study therapy or placement of an indwelling catheter, unless associated with other SAEs)
- Prolongation of existing hospitalization
- Persistent or significant incapacity or substantial disruption of the ability to conduct normal life functions

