#### **6.4 Missing Values**

For all patients enrolled and all activities and assessments performed, every effort will be made to achieve complete data collection. Imputation is not planned for missing data, other than for missing date/time values. The missing component(s) of incomplete dates (e.g. start or stop dates of TEAEs, concomitant medication use, events/conditions in medical history) will be assumed to be the most conservative value possible. For example, if the start date is missing the day value, then the first day of the month will be imputed for study day computations. If the end date is missing the day value, then the last day of the month will be imputed. A similar approach will be used for missing month and year components. For complete dates but missing start or end times, values marking the beginning of the day (00:00:00AM) or end of the day (23:59:59PM), respectively, will be imputed. Importantly, date/time imputation will be used for computational purposes only; actual data values (as they appear in the database) will be presented in all patient-level data listings. Patients who withdraw consent for study participation or are lost to follow-up will be included in data summaries and analyses to the point of last contact.

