## **8.5 Physical Examinations**

Multiple physical examinations will be performed during the period of screening through the Day-6 visit. Findings deemed clinically significant during screening will be recorded as medical history, whereas clinically-significant findings from all later exams will be captured as TEAEs. To disclose the details of all exam findings, regardless of clinical significance, a patient-level data listing will be provided.

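### SAP 6.3 splits adverse events into pre-treatment and treatment-emergent by timing alone, and does not say how to class one that is present before infusion and then worsens or becomes serious

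*SAP*

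**What the plan says.** The working definition is in SAP 6.3: "pre-treatment events occurring prior to start of the Thrombosomes infusion on Day 1 and treatment-emergent events occurring at or following the start of infusion". SAP 3.2 repeats the split, describing each AE by "timing of the event relative to infusion start (pre-treatment AE vs. treatment-emergent AE [TEAE", and SAP 8.1 tabulates by it.

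The definition feeds the first primary endpoint in SAP 2.2.1: "Overall frequency of (and number and percentage of patients who experience) TEAEs and TESAEs". SAP 2.1.1 lists a further kind of safety indicator beside TEAE and TESAE incidence, beginning with "abnormality or worsening in measures of bleeding severity" and going on to laboratory, vital-sign, cardiac, physical and neurologic measures.

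Three other places bear on how a record is dated or classed:

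- **SAP 6.4**, on incomplete dates: "if the start date is missing the day value, then the first day of the month will be imputed for study day computations". A missing start time is set to the beginning of the day.
- **Protocol 1.15.6.2**: the items on the Adverse Event Form include one start date and one stop date. No date of worsening or of becoming serious is listed.
- **SAP 8.5**: "Findings deemed clinically significant during screening will be recorded as medical history". Clinically significant findings at later exams become TEAEs.

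Neither document addresses an event or condition that exists before infusion and increases in grade or becomes serious afterwards.

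**The concern.** The patients have acute leukemia, myelodysplasia, or marrow aplasia or hypoplasia (Protocol 1.11.1), and are bleeding and thrombocytopenic. Many will have signs and symptoms at entry. For them, harm from an infusion may show as an increase in something already present rather than as a new event.

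Take a patient with a Grade 1 headache recorded at the Day 1 baseline that reaches Grade 3 or leads to hospitalization after infusion. If the record keeps its first start date, a timing-only rule makes it a pre-treatment AE, although the part that matters happened after exposure. The trial's first primary endpoint is the frequency of TEAEs and TESAEs by dose level, so the rule for entering that count should be explicit. With 8 patients per cohort, one record classed differently is visible in the result.

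**Working it through.** The plan states no figure to reproduce. The sample size is not statistically derived (SAP 4), and the documents give no rate of worsening. The check is therefore of the text, followed by arithmetic for scale.

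**Step 1. Does the definition cover worsening?** SAP 6.3, 3.2 and 8.1 use timing relative to infusion start and nothing else. No section adds a condition on grade or seriousness. SAP 6.3 does not exclude worsening either: its word is *occurring*, not *beginning* or *new*.

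**Step 2. Which date would a programmer use?** Two places point to the original start date. The AE form items in Protocol 1.15.6.2 hold one start date, and SAP 6.4 imputes start dates to compute study days. Neither document tells sites to open a new line when an event worsens. This supports classification by start date as the likely outcome, but does not establish it.

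**Step 3. What follows if the start date is used?** In SAP Appendix 2, Tables 14.3.1.2 to 14.3.1.9 (eight tables) are limited to TEAEs. Tables 14.3.2.1 to 14.3.2.7 (seven) are limited to TESAEs, and 14.3.2.8 to treatment-emergent deaths. An event that began before infusion and became serious afterwards would then be left to the all-AE summary (14.3.1.1) and the listings. Three of the DMC outputs in SAP Appendix 1 are TEAE or TESAE summaries.

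**Step 4. What captures worsening by another route?**

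- WHO bleeding grade increases, and shifts to clinically significant laboratory or EKG results, are primary endpoints of their own (SAP 2.2.1).
- Clinically significant physical-exam findings after screening become TEAEs (SAP 8.5).
- Protocol 1.22.6.1 excuses only mild, not clinically significant laboratory changes from being AEs. It makes complications in hospital AEs, and SAEs if they prolong the stay. These rules settle what is an AE or SAE, not whether it is treatment-emergent.
- Vital signs and oxygen saturation get descriptive statistics with no shift table (SAP 8.4). A symptom such as headache has no parallel measure.

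**Step 5. Scale.** With 8 patients per cohort and 24 in all (SAP 3.1), a patient who has no other qualifying TEAE moves an incidence by 1/8 = 12.5 percentage points in a cohort, or 1/24 = 4.2 points overall.

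Let q be the share of patients with a worsened pre-infusion event classed by its original start date. This share is an assumption. With patients taken as independent, the expected number is n × q, and the chance of at least one is 1 − (1 − q)^n; for example, 1 − 0.95^8 = 0.337.

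| Assumed q | Expected, n = 8 | At least one, n = 8 | Expected, n = 24 | At least one, n = 24 |
|---|---|---|---|---|
| 5% | 0.4 | 34% | 1.2 | 71% |
| 10% | 0.8 | 57% | 2.4 | 92% |
| 20% | 1.6 | 83% | 4.8 | 99.5% |
| 30% | 2.4 | 94% | 7.2 | >99.9% |

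These are chances that the question arises, not estimates of bias.

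**The case against.** A reader might infer that SAP 6.3 counts only events that begin after infusion, so that worsening is excluded by rule. The text does not say that. A worsening entered as a separate AE dated after infusion counts under 6.3 as written. A condition held as medical history that deteriorates after infusion can also meet the AE definition in Protocol 1.22.6.1, with a post-infusion date. SAP 1 refers the reader to the case report forms for data collection methods; they are not among the documents, so sites may be instructed there.

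The exposed group may also be small. In Protocol Table 4 and SAP Table 2, AE monitoring starts at the Day 1 baseline, so pre-treatment AE records should come mainly from the hours before infusion.

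Nor is SAP 2.1.1 in contradiction with 6.3. It attaches worsening to measures, separately from TEAE incidence, and 2.2.1 gives several of those measures their own endpoints.

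A reader might also infer that escalation decisions would miss such events. SAP Appendix 1 has the DMC review all SAEs and AEs. It also receives a summary of AEs, a listing of at least possibly related SAEs, and laboratory listings. The suspension and stopping rules (Protocol 1.9.8, SAP 3.2) act on SAEs and relatedness, not on the TEAE flag.

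Finally, a reader might put a bias figure on the gap. Supposing one to three affected patients in a cohort gives 12.5 to 37.5 points, but nothing in the documents supports that count. The overall patient-level TEAE percentage moves only if the patient has no other TEAE at all.

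All of this stands, and it limits the point. It does not remove it: the definition behind a primary endpoint is silent on a foreseeable case, and what the documents say about dates leans towards leaving that case out.

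**Conclusion.** SAP 6.3 leaves unspecified how to class post-infusion worsening of an event or condition present before infusion. It is a gap in the definition, not a stated exclusion. If records are classed by original start date, such events are missing from the primary TEAE/TESAE counts and the tables built on them. Relative to a definition that includes worsening, that can only lower the counts.

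The amount is unknown. The unit is 12.5 points per affected patient in a cohort of 8 and 4.2 points in 24, provided the patient has no other TEAE that qualifies for the same row. By-term, Grade 3 or higher, and TESAE rows are more exposed than the any-TEAE row, because patients may well have some other TEAE.

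The conclusion rests on two assumptions: that the original start date drives the classification, and that no site instruction outside these documents settles the matter. Patient protection through the stopping rules and DMC review is not affected. This should be corrected as a cheap improvement to the primary safety summary, and does not put the trial in doubt.

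**What to change.** Before database lock:

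1. Rewrite SAP 6.3 so that a TEAE is an AE that starts at or after the start of infusion, or that was present before it and increases in CTCAE grade or becomes serious at or after that time.
2. Set TESAE status by the date on which the event became serious.
3. Instruct sites, in the CRF completion guidance, to enter a post-infusion worsening as a new AE line with the date of worsening.
4. Apply the same definition to the TEAE and TESAE tables supplied to the DMC.

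Two related places should be settled in the same edit. SAP 6.4 should say that an event whose partial date or time cannot place it before or after infusion is treated as treatment-emergent; at present a Day 1 event with no start time is set to midnight, which is before infusion. SAP 8.5 should be aligned with 6.3, because the exams after screening include the pre-infusion rescreen and baseline exams, and their findings are not treatment-emergent under 6.3.

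The cost is SAP wording, one CRF instruction and a small derivation change. The reported TEAE rate may become slightly less favourable.

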#### **6.4 Missing Values**

For all patients enrolled and all activities and assessments performed, every effort will be made to achieve complete data collection. Imputation is not planned for missing data, other than for missing date/time values. The missing component(s) of incomplete dates (e.g. start or stop dates of TEAEs, concomitant medication use, events/conditions in medical history) will be assumed to be the most conservative value possible. For example, if the start date is missing the day value, then the first day of the month will be imputed for study day computations. If the end date is missing the day value, then the last day of the month will be imputed. A similar approach will be used for missing month and year components. For complete dates but missing start or end times, values marking the beginning of the day (00:00:00AM) or end of the day (23:59:59PM), respectively, will be imputed. Importantly, date/time imputation will be used for computational purposes only; actual data values (as they appear in the database) will be presented in all patient-level data listings. Patients who withdraw consent for study participation or are lost to follow-up will be included in data summaries and analyses to the point of last contact.

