**Table 4. Schedule of Events**

Evaluation	Initial Screen	Rescreen (if applicable  )	Day 1  Base Line -2 hr pre-infusion	1 hr post infusion ± 15min	6 hr post -1 or +2 hr	Day 2 24 hr post ± 3 hr	If hospitalized			Day 6 (+ 4 days)	Day 30 (+2 days) (by phone)
							Day 3	Day 4	Day 5		
Visit #	1	1A	2	3	4	5	6	7	8	9	10
Sign ICF	X										
Verbal reconfirmation of informed consent		X	X	X	X	X	X	X	X	X	X
History and complete physical exam 	X										
WHO assessment	X	X	X	X	X	X				X	
Abbreviated physical exam 		X	X	X	X	X				X	
Pregnancy test (serum or urine)-applicable females only	X	X									
Concomitant medications (Medications, OTC Remedies, Herbal Preparations,	X	X	X	X	X	X	X	X	X	X	

Evaluation	Initial Screen	Rescreen (if applicable  )	Day 1  Base Line -2 hr pre-infusion	1 hr post infusion ± 15min	6 hr post -1 or +2 hr	Day 2 24 hr post ± 3 hr	If hospitalized			Day 6 (+ 4 days)	Day 30 (+2 days) (by phone)
							Day 3	Day 4	Day 5		
Vitamins, Supplements and IV fluids)											
Record transfused blood products 	X	X	X	X	X	X	X	X	X	X	
Infusion			X								
Vital signs (pulse, BP, RR, temp)	X	X	X	Prior to infusion and then every 15 min ±5 min after the start of infusion until 2 hrs; continue every hour ±5 min until 4 hrs, then at 6 hrs, and 24 hrs post infusion.						X	
Pulse-Ox			X	Continuously monitor while monitoring for vital signs; record at same time points as for vital signs above.							
Monitor for AE			X	Prior to infusion and then every 15 min ±5 min after the start of infusion until 2 hrs; continue every hour ±5 min until 4 hrs, then at 6 hrs, and 24 hrs post infusion, ±10 mins for all other time points. Daily until discharged or Day 6.			X	X	X	X	X 
12-Lead EKG	X		X 		X						

Evaluation	Initial Screen	Rescreen (if applicable  )	Day 1  Base Line -2 hr pre-infusion	1 hr post infusion ± 15min	6 hr post -1 or +2 hr	Day 2 24 hr post ± 3 hr	If hospitalized			Day 6 (+ 4 days)	Day 30 (+2 days) (by phone)
							Day 3	Day 4	Day 5		
Hematology CBC (if blood products are transfused, then CBC pre and post transfusion)	X	X	X	X	X	X	Minimum is daily CBC			X	
ABO group, Rh type	X										
Coagulation Tests: PT/INR, aPTT, D-dimer, Fibrinogen, TAT, PF 1+2, TEG or ROTEM, TGA	Only PT/INR, aPTT, D-dimer, Fibrinogen	Only PT/INR, aPTT, D-dimer, Fibrinogen	X	X	X	X					

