#### **1.15.6.2 *Blood Sampling/Testing***

- A. Additional tests for evaluation and/or treatment of safety and/or laboratory events may occur. The additional tests will be determined by the patient's signs, symptoms or review of laboratory data, and will not be dictated by the protocol. A recommendation for the need for additional testing will be made by the patient's treating physician. The patient must agree to the additional tests before these tests can be performed.
- B. Label all blood tubes following sites standard operating procedures (SOP) and patient study ID number, date, time and visit number.
- C. Send samples for testing following site's SOP.

D. Complete Adverse Event Form that includes description of the event, relatedness, start date, stop date, medications used to treat and results of laboratory testing.

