## 7.4 Prior and Concomitant Medications

The use of prior medications and concomitant medications will be summarized in separate tables as the numbers and percentages of patients in the Safety Population who used medication within each reported hierarchy of WHO Drug Anatomical-Therapeutic-Chemical (ATC) Levels 1, 2, and 3 and WHO Drug preferred name. Medications with partial start and/or stop dates, which cannot be definitively categorized as prior or concomitant, will be considered concomitant. The details of prior and concomitant medication use will be disclosed in a single patient-level data listing.

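### SAP 6.4 sets a missing onset time to midnight, so a post-infusion adverse event dated Day 1 with no time is classed as pre-treatment

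*SAP*

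**What the plan says.** SAP 6.3 counts as treatment-emergent those "treatment-emergent events occurring at or following the start of infusion"; anything earlier is pre-treatment. No other criterion is given. Infusion takes place on Day 1 (SAP 6.2), so hours before and after infusion share one calendar date.

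SAP 6.4 imputes missing dates and times for computation only; listings keep the recorded values. For times the rule is "For complete dates but missing start or end times, values marking the beginning of the day (00:00:00AM" for a start, and the end of the day for a stop. Incomplete dates are to take the most conservative value, illustrated by "if the start date is missing the day value, then the first day of the month will be imputed for study day computations".

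For medications, SAP 7.4 adds a default: "Medications with partial start and/or stop dates, which cannot be definitively categorized as prior or concomitant, will be considered concomitant". SAP 6.3, 6.4 and 8.1 contain no equivalent for adverse events.

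SAP 3.2 says events will be described by "timing of the event relative to infusion start (pre-treatment AE vs. treatment-emergent AE [TEAE"), but neither document shows whether the case report form records this directly. The first primary endpoint in SAP 2.2.1 is "Overall frequency of (and number and percentage of patients who experience) TEAEs and TESAEs".

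**The concern.** The earliest possible onset is a cautious choice for event duration. It is the opposite for deciding whether an event followed treatment. On Day 1, midnight always falls before the infusion, so the imputation decides the classification, and always in the same direction: a true post-infusion event can be moved out of the TEAE count, and no pre-infusion event can be moved in.

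Day 1 is the day of closest surveillance and the day on which acute infusion reactions would appear. An event moved this way drops out of the primary-endpoint counts and out of the TEAE and serious-TEAE tables that the Data Monitoring Committee receives before advising on escalation (SAP Appendix 1).

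**Working it through.** The plan states no figure for this point. The check applies its two rules to concrete cases.

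**1. Missing time, complete date.** Inputs: imputed onset is Day 1 at 00:00:00 (SAP 6.4); an event is pre-treatment if onset precedes infusion start (SAP 6.3). Over the 1,440 possible infusion-start minutes of a day, midnight precedes infusion in 1,439. The only exception is an infusion starting exactly at 00:00. In practice, every untimed post-infusion event dated Day 1 becomes pre-treatment.

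**2. Missing day.** This is an inference, because the first-of-month rule is offered as an example for study-day computation. Inputs: all 516 infusion dates from 1 January 2018 to 31 May 2019 (within the study span in protocol 1.4), onsets spread evenly over the stated study days (an assumption), and the onset day imputed as the 1st of the onset month. The lower figure counts imputed dates before the infusion date. The upper figure also counts imputed dates equal to it, since a midnight time still precedes infusion.

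| True onset | Classed as pre-treatment |
|---|---|
| Days 1-10 | 81.9% to 85.2% |
| Days 11-32 (only serious events are tabulated after the Day-6 visit) | 29.6% to 32.6% |

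These shares apply only to events with no recorded onset day.

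**3. How much of the scheduled monitoring falls on Day 1.** From protocol Table 4, the adverse event checks after infusion start are every 15 minutes to 2 hours (8), at 3 and 4 hours (2), and at 6 hours (1): 8 + 2 + 1 = 11 on Day 1, if infusion starts before 18:00. The later checks are described as "then at 6 hrs, and 24 hrs post infusion, ±10 mins for all other time points. Daily until discharged or Day 6".

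- Inpatient: 11 + 1 (24 h) + 3 (Days 3-5) + 1 (Day 6) = 16, and 11/16 = 69%.
- Outpatient: 11 + 1 (24 h) + 1 (Day 6) = 13, and 11/13 = 85%.

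These are shares of scheduled checks, not of events or of missing times.

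**4. Effect of one misplaced event.** SAP 3.1 plans three cohorts of 8. If the event is the patient's only TEAE, the rate falls by 1/8 = 12.5 percentage points in the cohort and by 1/24 = 4.2 points overall. Otherwise only the event count falls.

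**Not affected:** complete onsets, events dated Day 2 or later with only the time missing, and missing-day events in a month after the infusion month.

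**The case against.** - **Imputation may not be meant to decide TEAE status.** SAP 6.4 lists TEAE dates among those to be completed, which could mean that status is assigned first, and the one use it names for a start date is the study day, which does not depend on the time. But 6.4 says imputed values serve computation generally, 6.3 offers only the onset comparison, and the time rule stands apart from the sentence on conservative values. If status were assigned first, the plan would have no rule at all for an untimed Day 1 event.
- **The form may capture onset time or timing relative to infusion.** It may. Frequent Day 1 checks and the 48-hour and 4-hour stopping limits suggest that times will often be known. That bears on frequency and is accepted. The one description of the form in the documents, in protocol 1.15.6.2 for unscheduled visits, reads "Complete Adverse Event Form that includes description of the event, relatedness, start date, stop date, medications used to treat and results of laboratory testing" and names no time; the form itself is not shown.
- **SAP 7.4 is not a like-for-like precedent.** Correct: it concerns partial dates, not missing times. It shows the principle only.
- **The denominators may be larger.** TEAE tables use all infused patients, and protocol 1.10.1 expects about 30 enrolled. With 30 infused and evenly split, the effect is 1/10 = 10 points in a cohort and 1/30 = 3.3 points overall. This is a fair qualification.
- **SAP 8.5 already sends clinically significant findings from later physical exams to TEAE.** That covers one source of events and says nothing about missing times.

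**Conclusion.** The concern holds and should be fixed before database lock. Following SAP 6.3 and 6.4 as written gives the wrong class to a post-infusion event dated Day 1 with no time, and nothing else in the documents corrects it. The missing-day route is likely but remains an inference.

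The size is limited. How often onset times will be missing cannot be known from the documents and is probably low if they come from the Table 4 checks. One affected patient changes a cohort rate by 12.5 points with 8 infused, or about 10 points with 10 infused. The events are relabelled, not lost: they stay in the all-event summary, which the committee also receives, and in the listings with their recorded dates. The suspension and stopping rules do not depend on TEAE status, and data validation and cleaning may catch some cases.

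**What to change.** Add to SAP 6.4:

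> An AE with an incomplete onset date/time is a TEAE unless its recorded onset components, its recorded stop date/time, or its recording at a pre-infusion assessment show that it began before infusion start. For such a TEAE, the imputed onset is the later of the value imputed under this section and infusion start; assignment to the through-Day-6 or after-Day-6 summaries follows the visit at which it was reported, as in 8.1. Complete onsets are not altered.

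Worked through twelve cases with infusion on 20 June 2018 at 10:00, the wording behaves as intended:

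| Recorded data | Current rules | With the fix |
|---|---|---|
| 20 June, no time; same with stop on 20 June, no time; June, no day; 2018 only | Pre-treatment | TEAE, onset 20 June 10:00 |
| 20 June, no time, recorded at the pre-infusion check; 20 June, no time, stopped 20 June 08:00; June, no day, stopped 19 June; May, no day; 19 June, no time | Pre-treatment | Pre-treatment |
| July, no day; 23 June, no time; 23 June 09:00 | TEAE | TEAE, onset unchanged |

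A minor companion edit belongs in SAP 8.5. Its reference to exams after screening can be read to include the Day 1 pre-infusion exam, which does not fit 6.3. Limit TEAEs there to clinically significant findings with onset at or after infusion start.

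The cost is three sentences in 6.4 and one in 8.5, with no new assessments. A few events that truly began before infusion may be counted as TEAEs, which is the cautious direction for a Phase 1 safety study. If the database does not show that an event was recorded at the pre-infusion check, that exception cannot be used; unless its recorded onset or stop data show an earlier start, the event defaults to TEAE.
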